- Virological criterion: persistently positive SARS-CoV-2 PCR \geq 21 days.

Although 21 days may not be a particularly long duration in this type of patient, in this study we will use this time reference to identify patients with persistent infection.

Current COVID-19 treatment guidelines recommend the use of a single agent within few days of symptoms for all the patients with mild disease but with risk factors for progression

to severe disease, including immunocompromised condition. Remdesivir remains the only approved antiviral to treat hospitalized patients with COVID-19 in case of progression to LRTI and, in any case, after 10 days from diagnosis patients are no longer eligible for any treatment. Moreover, specific indications for immunocompromised patients are limited to the use of long-acting monoclonal antibodies as SARS-CoV-2 pre-exposure prophylaxis for individuals who may have an inadequate immune response to COVID-19 vaccination. It should also be specified that there is currently insufficient evidence to guide clinical recommendations for other treatments in immunocompromised patients [7].

However, in clinical practice, it appears clear that such recommendations are not sufficient to guarantee the cure of SARS-CoV-2 infection in immunocompromised patients, in particular in the “long persisters” population. Currently in literature, only case reports or small case series have described the prevalence and the management of patients with persisting infection. These studies show a wide variability of therapeutic approaches ranging from the adoption of repeated or prolonged cycles of remdesivir [8-10] or nirmatrelvir/ritonavir [11], dual antiviral therapy [12-13] and combination therapy with antiviral and monoclonal antibodies [14-16]. These case reports show variable success rates and highlight the need for larger studies focused on immunocompromised patients, to identify the best therapeutic approach in this population.

With this premise, we would like to conduct an observational study on immunocompromised patients, and specifically on haematological patients with B cell malignancies diagnosed with SARS-CoV-2 infection, with the aims of assessing the prevalence of those with persisting COVID-19, associated risk factors and describe the different clinical managements and their related outcomes.

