4.3 Study design

Spontaneous international multicenter retrospective and prospective observational study.

The retrospective recruitment period will span from 1.01.2022 to the date of authorisation by hospital directorates following the Ethics Committees' approvals. This period has been established considering the prevalent diffusion of the omicron variant and its subvariants, which has led to significant changes in the clinical manifestations of COVID-19. The prospective recruitment will be carried out over the 12 months immediately following the retrospective period.

During the study period, screening for persisting SARS-CoV-2 infection and therapeutic management of all patients will be carried out by the attending physicians according to routine practice.

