4.8 Statistical Analysis Plan

Patients' characteristics will be summarized using absolute frequencies and percentages (categorical variables) and mean±standard deviation or median and interquartile range (scale variables, according to their distribution).

The prevalence of persisting SARS-CoV-2 infection among the immunocompromised patients will be obtained as the ratio of the number of patients with evidence of persisting SARS-CoV-2 infection on the total number of enrolled patients.

As for the analysis of risk factors for persisting COVID, comparisons between COVID-persistent and non-persistent patients will be carried out by means of survival analyses for all outcomes expressed as durations (time-to-event analyses). These outcomes will be compared by estimating Kaplan-Meier curves, calculating log-rank tests and multiple Cox regressions in which COVID persistence will be the main risk factor and including the confounders and effect modifiers listed below.

- Age
- Sex
- Comorbidities (Charlson Comorbidity Index)
- Underlying hematologic disease state
- Chemotherapy treatments performed
- Duration of Hospital stay
- Admissions to intensive care
- Days with central venous catheter
- Bacterial and fungal superinfections
- Vaccination status
- Previous SARS-CoV-2 infections
- Serological status (anti-SARS-CoV-2 antibodies)

Re-infection and imaging alterations rates will be calculated as the ratio of the number of events to the overall number of patients, and the comparison between persisters and non-persisters will be carried out by calculating the corresponding risk ratios. A multiple logistic regression model will assess the relationship between exposure and re-infection (image alteration) net of the potential confounders.

For secondary aims, the secondary endpoints will be described just for the patients with persisting COVID, categorical variables will be reported as number and relative

frequencies, continuous variables will be reported as mean±SD or median and IQR according with their distribution.

5. Administrative procedures and declarations

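### The Cox adjustment list leaves out centre, calendar period and early antiviral or antibody treatment, so the comparisons of persisters with non-persisters may be confounded by site practice and period

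*Combined protocol and SAP*

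**What the plan says.** Section 4.8 (Statistical Analysis Plan) describes multiple Cox regressions in which "COVID persistence will be the main risk factor and including the confounders and effect modifiers listed below". Twelve items follow: age, sex, the Charlson index, disease state, chemotherapy, length of hospital stay, intensive care, catheter days, superinfections, vaccination, earlier SARS-CoV-2 infection and serology. The only treatment among them is "Chemotherapy treatments performed". For re-infection and imaging, the same section says: "A multiple logistic regression model will assess the relationship between exposure and re-infection (image alteration) net of the potential confounders". It gives no separate list for that model.

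Section 4.3 (Study design) sets the calendar span: "The retrospective recruitment period will span from 1.01.2022", continuing to local authorisation, and "The prospective recruitment will be carried out over the 12 months immediately following the retrospective period". It says the period was chosen "considering the prevalent diffusion of the omicron variant and its subvariants, which has led to significant changes in the clinical manifestations of COVID-19". It also leaves screening for persistence and therapy to the attending physicians' usual practice.

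Section 2.1 notes: "Current COVID-19 treatment guidelines recommend the use of a single agent within few days of symptoms", for patients with mild disease and risk factors, among which it counts immunocompromise. Section 4.4.3 forecasts about 500 of some 1,000 patients from the coordinating centre.

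**The concern.** Under section 3.3, a patient counts as a persister only with a positive PCR at 21 days or later plus symptoms or signs. Where re-testing follows local habit, the centre helps decide who is classed as exposed. Centres can also differ in case mix, care and mortality. Calendar period works in a similar way: circulating subvariants, available treatments and testing intensity may all change over a window of more than a year. Early antiviral or antibody treatment could affect both clearance by day 21 and death.

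A factor that moves both classification and outcome, and is not in the model, can produce or hide a difference between the groups. The 120-day mortality comparison is most exposed, because the sample size was justified on it. The other comparisons that take persistence as the exposure share the problem. Period and centre are ordinary adjustment terms in a multicentre cohort with a retrospective and a prospective phase, so their absence stands out.

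**Working it through.** **1. What the list covers.** Set against the sources of variation that the protocol itself describes:

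| Source of variation | Where described | In the 4.8 list? |
|---|---|---|
| Centre practice in testing and therapy | 4.3; about half of patients from one centre, 4.4.3 | No |
| Calendar period or subvariant | 4.3 | No, though vaccination, earlier infection and serology may partly track it |
| Retrospective or prospective recruitment | 4.3; different consent routes, 5.1.1 | No |
| Early antiviral or antibody treatment | 2.1; therapeutic approaches are a comparison in 3.2 | No |

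No other section uses these as adjustment, stratification or clustering terms.

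**2. The plan's own figure.** The table in section 4.4.3 uses Freedman's log-rank method with k = 0.43, two-sided alpha 0.05 and 80% power. For 3% versus 7% mortality:

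- HR = ln(0.93)/ln(0.97) = 2.383
- E = (1.960 + 0.842)² × (1 + k·HR)² / [k(HR − 1)²] = 39.1 deaths
- Pr(E) = (0.03 + 0.43 × 0.07)/1.43 = 0.0420
- N = 39.1/0.0420, or 932 without intermediate rounding (table: 933)

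The 4% versus 9% row gives 768 (table: 768; HR 2.310), and the 5% versus 10% row gives 896 (table: 897; HR 2.054). The table is sound for an unadjusted test and is not in dispute.

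Expected deaths with 700 and 300 patients are 700 × 0.03 + 300 × 0.07 = 42, then 28 + 27 = 55, and 35 + 30 = 65.

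**3. Size of a possible bias.** The documents give no treatment uptake and no mortality by treatment, so every input here is an assumption. Let persistence have no effect on death, and let early treatment be the one omitted factor.

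Worked case: 60% treated; persistence 20% treated, 45% untreated; mortality 2.5% and 7%.

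- Persisters: 0.60 × 0.20 = 0.12 treated and 0.40 × 0.45 = 0.18 untreated. Mortality = (0.12 × 2.5% + 0.18 × 7%)/0.30 = 5.2%.
- Non-persisters: 0.48 treated and 0.22 untreated. Mortality = (0.48 × 2.5% + 0.22 × 7%)/0.70 = 3.9%.
- Apparent ratio = 1.33.

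| Treated | Persistence, treated / untreated | Mortality, treated / untreated | Apparent ratio |
|---|---|---|---|
| 60% | 20% / 45% | 2.5% / 7% | 1.33 |
| 50% | 20% / 40% | 3% / 6% | 1.17 |
| 50% | 15% / 45% | 2% / 8% | 1.49 |
| 90% | 20% / 45% | 2.5% / 7% | 1.21 |
| 90% | 20% / 40% | 3% / 6% | 1.10 |

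The first three rows keep overall persistence at the 30% used in section 4.4.3. The last two give 22.5% and 22%.

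**4. The same question for any binary factor**, such as a centre group or period. With mortality ratio g and prevalence p1 in persisters and p0 in non-persisters, apparent ratio = [1 + p1(g − 1)]/[1 + p0(g − 1)].

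| g | 50% v 40% | 60% v 40% | 70% v 30% |
|---|---|---|---|
| 1.5 | 1.04 | 1.08 | 1.17 |
| 2 | 1.07 | 1.14 | 1.31 |
| 3 | 1.11 | 1.22 | 1.50 |

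Swapping p1 and p0 inverts each ratio, giving 1/1.50 = 0.67 to 1/1.04 = 0.96. The bias can run in either direction.

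**5. Against the effect the study is sized for.** On the log scale, ln(1.10)/ln(2.383) = 0.095/0.868 = 11%, and ln(1.49)/ln(2.054) = 0.399/0.720 = 55%.

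**The case against.** The case on the other side has real force.

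- **Era is partly handled.** Starting in January 2022 is itself a restriction to the omicron period, and vaccination, earlier infection and serology plausibly follow calendar time. This stands: what remains is subvariant and period variation within that era.
- **The size is assumed.** A reader might infer that the comparisons are shown to be confounded, and upward. The documents do not support that. They contain no uptake or effect data, and sicker patients being treated preferentially could weaken or reverse the bias. With 90% treated, the ratio falls to 1.10 to 1.21.
- **Availability.** A reader might infer that every omitted item is on file for all patients. Time 0 is the first positive test (3.3) and centres enter their own data (4.7), so date and centre should usually exist. The eCRF fields are not shown, however. The only treatment endpoint concerns therapy for the persistent condition, and section 5.1 allows anonymised records for deceased or untraceable patients, some of which may lack fields.
- **Scope.** A reader might extend the point to the prevalence estimate. That is a crude ratio; uneven re-testing would affect it through under-ascertainment, which no covariate corrects. Nor does section 4.8 specify a model with persistence as the outcome. The list is attached to the Cox models, and whether it also governs the logistic models is not stated.
- **Redundancy and cost.** Within a centre, recruitment mode follows from date, so adding both gains little. Deaths are few.

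The omission of centre and period survives all of this. Nothing in the plan stands in for centre, and the proxies for period are partial.

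**Conclusion.** The point holds as a possible, not a demonstrated, source of bias. As written, the Cox models compare persisters with non-persisters without accounting for centre, calendar period or early anti-SARS-CoV-2 treatment, although the protocol describes variation in each. The comparisons of mortality and other secondary outcomes may be confounded as a result. Size and direction cannot be derived from the documents. With no true effect and the assumed inputs shown, one omitted factor gives an apparent mortality ratio of about 1.1 to 1.5; the mildest corner of the general grid gives 1.04, and reversed imbalances give values below 1. That is smaller than the planned hazard ratios of about 2.05 to 2.38, but large enough to alter the interpretation of a modest result. The sample size table and the prevalence endpoint are not affected by this point. Whether the listed items that arise after infection belong in the model is a separate question.

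**What to change.** In section 4.8:

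1. Stratify the Cox models by centre (at least coordinating versus other) and by broad, prespecified bands of the date of first positive test. Together these largely cover recruitment mode.
2. State the covariates of the logistic models, and include centre and period among them.
3. As a sensitivity analysis only, where the data are recorded, add anti-SARS-CoV-2 treatment started in the initial treatment phase, and report results with and without it. Section 2.1 describes no treatment eligibility beyond 10 days from diagnosis, which gives a natural limit for this covariate. Treatment begun later may be a response to non-resolution, and adjusting for it could distort the comparison.
4. State how records lacking dates or treatment fields will be handled.

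Cost: SAP wording and a small loss of precision. Stratification uses no coefficients, which matters because persistence plus twelve covariates at one parameter each already leaves 42/13 = 3.2 to 65/13 = 5.0 deaths per parameter. The treatment term lowers this to 42/14 = 3.0 to 65/14 = 4.6, in the sensitivity analysis only. Bands must stay broad: two centre groups by three periods would average 42/6 = 7 to 65/6 = 11 deaths per stratum. As a guide to the loss, if the adjusters explained 5% or 10% of the variation in persistence, the 932 for 3% versus 7% would become 932/0.95 = 982 or 932/0.90 = 1,036. That kind of cost applies to any adjusted model, including the one now planned. A two-level centre stratum will not separate practice among the other centres, so finer grouping is preferable where numbers allow.

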2.1 Background and rationale

Although the impact of COVID-19 has been significantly reduced thanks to the effectiveness of vaccination and antiviral treatments, the risk of breakthrough infection remains higher in the immunocompromised population [1].

Immunocompromised patients are at increased risk for SARS-CoV-2-associated morbidity and mortality due to immunologic deficits that limit normal immune response and viral clearance [2-3]. Furthermore, the type of immunosuppression and the treatments performed significantly impact the natural trajectory of the COVID-19 infection, as in the case of patients with impaired adaptive humoral immunity who are relatively protected from acute infectious toxicity but have a high risk of prolonged viral shedding, viral rebound, and chronic infection [2-3].

In this group of patients, also known as “long persisters”, we find especially haematological patients with B cell malignancies or undergoing B cell targeting therapies such as anti-CD20 and CAR-T cell therapy. These patients, in addition to the complications related to SARS-CoV-2 infection itself, represent a particularly interesting population as the lack of viral clearance can lead to delays in life-saving treatments.

Despite major advances in our understanding of COVID-19, there is still a lack of consensus on how to define the condition of persistent infection in immunocompromised patients, also called “protracted SARS-CoV-2 infection” or “persistent inflammatory sero-negative COVID” [4-5]. In particular, two recent studies have tried to distinguish this phenomenon from “long COVID-19” and “post-COVID-19 condition”, which is defined by the WHO as a syndrome that occurs in individuals who have contracted COVID-19 in the previous 3 months and have at least 2 months of ongoing symptoms (such as fatigue, dyspnoea, and cognitive dysfunction), with no alternative diagnoses [6]. Both studies [4-5] suggest the use of diagnostic criteria that combine baseline host immunodeficiency, clinical signs and virological data, which we can summarize as follows:

- Host criterion: underlying immunosuppression such as HCT, CAR T-cell recipient, lymphoma or B-cell malignancy, SOT, Anti-CD20 therapy or other B/T cell targeted therapies, primary and acquired immunodeficiencies.
- Clinical criterion: persistent/relapsing symptoms (fever, dyspnea, hypoxemia) and/or persistent/relapsing changes on chest-X ray or CT scan after extensive negative infectious work up.

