3.1 Primary objective

The primary objective of this study is to describe the prevalence of SARS-CoV-2 persisting infection and the related risk factors in immunocompromised patients with B cell malignancies or undergoing B cell targeting therapies.

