4.4.1 Inclusion Criteria

- Diagnosis of B cell malignancies or previous treatment with B cell targeting therapies.
- Diagnosis of proven SARS-CoV-2 infection confirmed by a PCR test (only the first infection during the study period will be considered, re-infection will be counted as a secondary endpoint).
- Provision of signed and dated informed consent.

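### The covariate list in section 4.8 does not name B-cell-targeting therapy, so the adjusted Cox comparisons of persisters and non-persisters may be confounded by it

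*Combined protocol and SAP*

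**What the plan says.** The primary objective (3.1) covers the prevalence of persisting infection and "the related risk factors in immunocompromised patients with B cell malignancies or undergoing B cell targeting therapies".

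The background (2.1) states that "the type of immunosuppression and the treatments performed significantly impact the natural trajectory of the COVID-19 infection". It places long persisters especially among haematological patients with "B cell malignancies or undergoing B cell targeting therapies such as anti-CD20 and CAR-T cell therapy". Its summary of host criteria includes transplant and CAR-T recipients and "Anti-CD20 therapy or other B/T cell targeted therapies".

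Eligibility (4.4.1) is either/or: "Diagnosis of B cell malignancies or previous treatment with B cell targeting therapies".

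Section 4.8 plans "multiple Cox regressions in which COVID persistence will be the main risk factor and including the confounders and effect modifiers listed below". Twelve items follow. Two concern the haematological condition or its treatment: "Underlying hematologic disease state" and "Chemotherapy treatments performed". No item names anti-CD20, CAR-T, transplant, any other B-cell-targeting therapy, or the time since such therapy. The logistic models for re-infection and imaging adjust for potential confounders, but no list is attached to them.

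**The concern.** By the protocol's own reasoning, B-cell-targeting therapy is plausibly related to both sides of the Cox comparison. Section 2.1 says that impaired humoral immunity gives relative protection from acute toxicity but a high risk of prolonged shedding. Therapy that depletes B cells may thus make persistence (the exposure) more likely and may also change mortality and the durations (the outcomes). When given before the first positive test it precedes both. That is the usual profile of a confounder, and the adjustment set does not name it.

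The chemotherapy item is not a safe substitute. It is undefined, and with no time window it could include treatment given after infection. Section 2.1 notes that failure to clear virus can delay treatment, so later chemotherapy may be a consequence of persistence.

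If the therapy is left out, an adjusted hazard ratio for persistence could partly reflect who had been B-cell depleted rather than the effect of persisting infection.

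**Working it through.** **1. The list against the rationale.** The 12 items are age, sex, Charlson index, haematologic disease state, chemotherapy, hospital stay, intensive care, catheter days, superinfections, vaccination, previous infection and serology. Items that name B-cell-targeting therapy: 0 of 12. No other section adds a covariate.

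**2. Does the therapy vary?** Yes, it can. Under 4.4.1 a patient may enter through a B-cell malignancy without such therapy, or through the therapy.

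**3. What is modelled?** In the Cox models persistence is the exposure. In the logistic models re-infection or imaging change is the outcome. No model has persistence as the outcome.

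**4. The design figure.** Section 4.4.3 gives N = 933 and 40 events for 3% versus 7% mortality (Freedman, two-sided 0.05, 80% power, ratio r = 0.43).
- HR = ln 0.93 / ln 0.97 = 2.383.
- E = (1.960 + 0.842)² × (1 + 0.43 × 2.383)² / (0.43 × 1.383²) = 39.1, rounded up to 40.
- Event probability = 1 − (0.97 + 0.43 × 0.93)/1.43 = 0.04203.
- N = 39.1/0.04203 ≈ 931, against 933 stated.

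The figure reproduces. It is for an unadjusted log-rank test.

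**5. Possible bias (all inputs assumed).** For one binary confounder with nothing else adjusted, the factor on the persistence ratio is [1 + p1(k − 1)]/[1 + p0(k − 1)]. Here p1 and p0 are the proportions treated among persisters and non-persisters, and k is the mortality ratio for therapy. With p1 = 0.6 and p0 = 0.3:
- k = 0.5: 0.70/0.85 = 0.82
- k = 2: 1.60/1.30 = 1.23
- k = 3: 2.20/1.60 = 1.38

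A second set of assumptions has therapy in 30–70% of the cohort, an odds ratio for persistence of 1.5–4, k of 1.5–3, and 30% persistent (the last from 4.4.3). A true ratio of 1.00 would then appear as 1.03 to 1.43:
- Low end (70% treated, odds ratio 1.5, k = 1.5): p1 = 0.757, p0 = 0.675, factor 1.03.
- High end (30% treated, odds ratio 4, k = 3): p1 = 0.513, p0 = 0.209, factor 1.43.

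**6. Cost of adjusting.** In the second set the squared correlation R² between therapy and persistence is about 0.01 to 0.09. Dividing 931 by (1 − R²), with unrounded R², gives about 938 to 1,027 patients. At N = 1,000 split 300/700, power for 3% versus 7% is:

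| R² | Power |
|---|---|
| 0 | 82.7% |
| 0.05 | 80.8% |
| 0.10 | 78.6% |

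**7. Events.** Expected deaths = 0.03 × 700 + 0.07 × 300 = 21 + 21 = 42. Persistence plus 12 covariates, at one parameter each at least, gives 42/13 = 3.2 deaths per term. One more term gives 42/14 = 3.0. A fuller set would be a four-level class (3 parameters), time since last dose, transplant and chemotherapy. That is 6 parameters in place of 1, and 42/18 = 2.3.

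**The case against.** **The chemotherapy item may be a loose label for all haematological treatment.** This stands in part. The item is undefined, so the documents do not show that it excludes anti-CD20 or CAR-T. But the protocol uses a separate term for B-cell-targeting therapy in 2.1, 3.1 and 4.4.1 and never folds it into chemotherapy. Even a broad reading leaves class and timing open.

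**Serology and disease state may carry part of the effect.** This stands. Section 2.1 gives impaired humoral immunity as the mechanism, so antibody status may capture some of it. The factors in the working ignore this, and the low end of 1.03 is negligible.

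**The list is not shown to govern the logistic models.** This stands. Their confounders are unspecified, so omission there is a gap in the text rather than a demonstrated exclusion.

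**A large set of therapy terms would overload the mortality model.** This stands, and it is why the fix uses few levels. Continuous time since last dose is also undefined for patients who never had the therapy.

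A reader might infer that this list is the reason the plan does not estimate the protocol's leading risk factor. The documents do not support that. Persistence is never an outcome, so no listed factor, not even age or vaccination, is estimated as a predictor of it. Sections 2.1, 3.1 and 4.4.1 name B-cell malignancy and B-cell-targeting therapy together and do not rank them.

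A reader might also infer that the therapy must already be recorded because it is an entry criterion. A patient who enters through a malignancy needs no therapy entry, and the eCRF is not in the documents.

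**Conclusion.** The point holds as a matter of confounding control. Followed as written, the adjusted Cox comparisons do not name a plausible pre-infection confounder that the protocol's own rationale stresses, and the nearest item is undefined in content and time.

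The size and direction are unknown. The factor of about 0.8 to 1.4 rests wholly on assumed prevalences and mortality ratios, with therapy as the only confounder. Partial capture by serology and disease state would bring it closer to 1. The direction could go either way, because 2.1 describes protection from acute toxicity alongside a higher risk of persistence.

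The prevalence estimate is not affected. The comparisons at risk belong to the secondary objective (3.2), although 4.8 introduces them as the risk-factor analysis. The absence of any model for persistence is a wider gap, and changing the covariate list would not close it.

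**What to change.** In section 4.8:

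1. Replace the chemotherapy item with anticancer and immunosuppressive therapy received before time 0. Within it, make B-cell-targeting therapy its own covariate with few levels: for example none / remote / recent before time 0, or anti-CD20 / CAR-T or transplant / other / none if counts allow. Define the cut-point in advance. List chemotherapy before time 0 separately.
2. State that the same terms enter the logistic models for re-infection and imaging.
3. Drop items that arise after time 0, such as duration of hospital stay, from the mortality model. A three-level therapy variable (2 parameters) plus chemotherapy (1) in place of one item adds 2 terms. Removing hospital stay takes off 1, giving 14 terms and 42/14 = 3.0 deaths per term at best. Other post-time-0 items could go for the same reason.
4. Add a regression with persistence at day 21 as the dependent variable, and include the therapy variable among its pre-specified candidates.

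The cost is a few degrees of freedom: about 2 to 4 power points per added term at R² of 0.05 to 0.10. The sponsor must also confirm that the eCRF captures therapy and its timing, which the documents do not show. This should be done early. Under 5.1.1, retrospective patients without consent may be recorded with no linking key, so a missing field might not be recoverable for them. Clinical charts are already a stated data source (4.7).
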